### 15.2.2 Secondary Efficacy Analysis

The observed and change from baseline values of secondary endpoints will be summarized using descriptive statistics such as n, mean, median, minimum, and maximum for continuous variables and count and percentages will be provided for categorical variables by treatment group and overall. Individual subject data listings for all secondary endpoints will be presented for ITT population. Secondary endpoints will also be compared between treatment groups on the ITT, and PP population; a two-sided 0.05 level of significance will be used for each endpoint:

- Days alive and heart failure event-free (hospitalization for heart failure or ED visits for heart failure) over 30 days will be compared using the non-parametric Wilcoxon rank sum test.
- Changes from baseline in patient global assessment via visual analog scale (VAS) across follow-up timepoints will be analyzed using a GEE model with treatment arm, timepoint and treatment by timepoint interaction as fixed effects, and the baseline value

of VAS as covariates. An unstructured covariance matrix structure will be used to model the within subject errors.

- Changes from baseline in composite congestion score across follow-up timepoints will be analyzed using a GEE model with treatment arm, and timepoint and treatment by timepoint interaction as a fixed effect, and the baseline value of congestion score as covariates. An unstructured covariance matrix structure will be used to model the within subject errors.
- Changes from baseline in 5-point Current Dyspnea Score across follow-up timepoints will be analyzed using a GEE model with treatment arm, and timepoint and treatment by timepoint interaction as a fixed effect, and the baseline value of 5-point Current Dyspnea Score as covariates. An unstructured covariance matrix structure will be used to model the within subject errors.
- A repeated measures analysis of 7-point Dyspnea Score across follow-up timepoints will be analyzed using a GEE model with treatment arm, and timepoint and treatment by timepoint interaction as a fixed effect. An unstructured covariance matrix structure will be used to model the within subject errors.
- Changes from baseline in health-related quality of life, measured by the KCCQ-12 Short Form Overall Summary Score, across follow-up timepoints will be analyzed using a GEE model with treatment arm, and timepoint and treatment by timepoint interaction as a fixed effect, and the baseline value of the KCCQ-12 Overall Summary Score as covariates. An unstructured covariance matrix structure will be used to model the within subject errors.
- Changes from baseline in serum creatinine across follow-up timepoints will be analyzed using GEE model with treatment arm, and timepoint and treatment by timepoint interaction as a fixed effect, and the baseline value of serum creatinine as covariates. An unstructured covariance matrix structure will be used to model the within subject errors.
- Changes from baseline in body weight across follow-up timepoints will be analyzed using a GEE model with treatment arm, and timepoint and treatment by timepoint interaction as a fixed effect, and the baseline value of body weight as covariates. An unstructured covariance matrix structure will be used to model the within subject errors.
- Changes from baseline in Six-Minute Walk Distance (6MWD) across follow-up timepoints will be analyzed using a GEE model with treatment arm, and timepoint and treatment by timepoint interaction as a fixed effect, and the baseline value of 6MWD as covariates. An unstructured covariance matrix structure will be used to model the within subject errors.
- Changes from baseline in the ReDS percent lung fluid measurement across follow-up time points will be analyzed using a GEE model with treatment arm, and timepoint and treatment by timepoint interaction as a fixed effect, and baseline value as covariates.

An unstructured covariance matrix structure will be used to model the within subject errors.

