## 2. STUDY DESIGN

This is a multicenter, randomized, open label, controlled study evaluating the effectiveness, and safety of the Furoscix Infusor versus continued medical therapy in patients with chronic heart failure and fluid overload requiring augmentation in diuretic therapy outside of an acute care setting. 51 subjects will be randomly assigned (2:1) to receive Furoscix (n=34) versus continued medical therapy (n=17). Within a single 24-hour period, the 80 mg dose can be repeated at the discretion of the investigator  $\geq 2$  hours after the completion of the first dose. Subjects should be transitioned back to their oral maintenance diuretic regimen when clinically indicated at the discretion of the investigator. After Subjects have been transitioned to their oral maintenance

diuretic regimen, additional doses of Furoscix can be prescribed during the 30-day study period as needed based on the presence of congestion symptoms (e.g., dyspnea, edema, and/or excess weight gain) as determined by the investigator. No more than 7 doses of Furoscix are permitted during the 30-day study period. Additional doses beyond 7 requires approval by the medical monitor. Over the initial 7 days, all subjects will receive daily clinic or phone follow-up by the study staff. Decision of treatment with Furoscix in the intervention arm (Furoscix On-Body Infusor) as well as changes in oral diuretic dosing in the continued medical therapy group will be determined by the treating physician in coordination with the study nurse. Safety labs will be done on Days 1, 3, 7 and 30.

Each Subject will complete Screening, Treatment, and Follow-Up Phases on an outpatient basis. During the Screening Phase, all Subjects who sign the informed consent form and satisfy the inclusion/exclusion criteria will be enrolled into the trial. Drug administration will start on the day of enrollment (same day as screening after all eligibility criteria have been confirmed) after randomization.

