### **4. SAMPLE SIZE**

Fifty-one (51) subjects will be included and randomly assigned in a 2 to 1 ratio to receive Furoscix (n=34) or continued medical therapy (n=17) in the home setting with 30 days of follow-up. Given the exploratory nature of this study, no formal power analysis of sample size was conducted.

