For categorical variables, data will be summarized using counts and percentages. The number [n] indicates the actual number of subjects with a particular value of a variable or event, which should always be less than or equal to the total number of subjects in the respective treatment group [N]. The number and percentage of subjects with missing values for a variable/category/event will also be presented for the resulting visits under the “Missing” category. Percentage will be obtained by:  $\% = (n/m) * 100$ , where m is the number of subjects present at that visit. Unless otherwise stated, all percentages will be expressed to one decimal place. The number and percentage of subjects will always be presented in the form XX (XX.X). Counts of zero in any category will be presented as “0” and if the percentage in any category to be presented is 100, it will be presented as “100”.

The laboratory assessment values that are LLOQ (lower limit of quantification) will be converted to numeric values such as “<1” = 1 or “<5” = 5.

Tables that involve statistical modeling will not be presented if the model fails due to excessive missing data (e.g., GEE model fails to converge).

When analyzing statistical models (e.g. GEE models), if the unstructured covariance structure fails to converge then different covariance structures (e.g., Exchangeable (EXCH/CS), Independence (IND), Autoregressive(1)) will be applied.

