## 15. STATISTICAL ANALYSIS

This is a multicenter, randomized, open label, controlled study evaluating the effectiveness and safety of the Furoscix Infusor versus continued medical therapy in patients with chronic heart failure and fluid overload requiring augmentation in diuretic therapy outside of the acute care setting. The SAP takes precedence over the protocol.

Unless otherwise specified, all baseline data, including demographic data and other clinical characteristics will be compared using descriptive statistics grouped by treatment group (Furoscix On-Body Infusor vs Continued Medical Therapy for Worsening Heart Failure). Change from baseline is the absolute change, unless stated otherwise; which then will be percentage change from baseline. Tables will include footnotes indicating definition implemented. Continuous data will be summarized by reporting the number of observations, mean, standard deviation, minimum, median, and maximum values. Categorical data will be described using frequency tables showing the number and percentage of subjects falling within a particular category. Shift tables will be given where appropriate to show change at follow-up compared to baseline values.

Between-group analyses of baseline characteristics will employ descriptive statistics. Mortality and morbidity events will be assessed using appropriate statistical tests. The primary endpoint will be compared between treatments using the Finkelstein-Schoenfeld Method, comparing components of the composite endpoint between patients hierarchically. Given the nature of the study, there will be no imputation of missing data on endpoints.

The primary endpoints including CV death at 30 days, HF hospitalization at 30 days, Urgent ED/Clinic visit at 30 days for WHF (defined as IV diuretics, augmentation of or new administration of metolazone), and change in NT-proBNP from baseline at 7 days will also be summarized and analyzed separately.

In general, secondary efficacy with follow-up timepoints will be analyzed using Generalized Estimating Equations (GEE) models.

Statistical tests will be performed at a two-sided alpha level of 0.05, unless otherwise specified. Given the nature of the study, there will be no adjustment for multiple comparisons.

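### GEE on 34 versus 17 subjects with no small-sample correction, no stated reference distribution and an unordered fallback: NT-proBNP and nine secondary analyses would run at about 6-8% rather than 5%

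*SAP*

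**What the plan says.** SAP section 15 sets the general rule: "secondary efficacy with follow-up timepoints will be analyzed using Generalized Estimating Equations (GEE) models". SAP 15.2.2 applies it to nine of the ten secondary endpoints; the exception, days alive and HF event-free, uses a Wilcoxon rank sum test. SAP 15.2.1.1 uses the same kind of model for percent change in NT-proBNP at Days 3, 7 and 30, and will report the least-squares mean treatment difference with standard error, 95% CI and p-value. Each model has treatment, timepoint and their interaction, plus the baseline value (no baseline term for the 7-point dyspnea score). For the covariance, "An unstructured covariance matrix structure will be used to model the within subject errors".

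SAP 7.1 adds that "if the unstructured covariance structure fails to converge then different covariance structures (e.g., Exchangeable (EXCH/CS), Independence (IND), Autoregressive(1)) will be applied". The structures are examples, with no order. The same section drops a table if its model fails because of excessive missing data.

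On inference, SAP section 15 says "Statistical tests will be performed at a two-sided alpha level of 0.05, unless otherwise specified" and "Given the nature of the study, there will be no adjustment for multiple comparisons". Missing endpoint data are not imputed. The SAP names SAS but no procedure or option. It does not say which standard errors are used, whether a small-sample correction applies, or whether the reference is normal or t.

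**The concern.** The empirical (sandwich) variance used in ordinary GEE is justified for a large number of independent subjects. With 51 subjects, 17 of them in one arm, it tends to be too small, and a normal reference makes no allowance for estimating it. Carried out in the ordinary way, the stated method would therefore not deliver its 0.05 level or 95% coverage.

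A second issue is the covariance matrix. Some endpoints have nine follow-up visits, and an unstructured matrix of that size is hard to estimate from 51 people. If it fails, the analyst chooses among structures after the data are in hand, and one of those named is independence.

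At stake are the pilot's own aims. SAP section 6 lists informing a pivotal trial and refining its endpoints and analytical methods, and intervals that are too narrow make those estimates look firmer than they are.

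**Working it through.** **Design figure.** SAP sections 2 and 4: 51 × 2/3 = 34 and 51 × 1/3 = 17, as stated. There is no power figure to reproduce.

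**Visits and correlations.** An unstructured matrix for T visits has T(T−1)/2 correlations.
- KCCQ-12, Days 7 and 30 (protocol 6.2.22): T = 2, so 1.
- NT-proBNP, Days 3, 7 and 30 (SAP 15.2.1.1): T = 3, so 3.
- CCS, Days 1, 3, 7 and 30 (protocol 6.2.16): T = 4, so 6.
- VAS and 7-point dyspnea, Days 1-7, 17 and 30 (protocol 6.2.19, 6.2.21): T = 9, so 9 × 8/2 = 36.

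**Null simulation.** 34 versus 17; identity-link GEE with visit, treatment by visit and one baseline covariate; unstructured working correlation; uncorrected sandwich with a normal reference. Assumptions, since the documents give no figures: exchangeable correlation 0.6 or AR(1) 0.7 or 0.8, and dropout of 0% or 15%. There were 1,500 to 4,000 trials per case, so Monte Carlo error is about ±0.7 to 1.3 points. The last column comes from a separate simulation with serial correlation 0.6 and complete data.

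| Visits | Last-visit difference | Joint test, all visits | Treatment-by-time test |
|---|---|---|---|
| 2 | 7.3% | 7.8% | 6.2% |
| 3 | 5.9% | 9.7% | 8.4% |
| 4 | 6.6% | 11.6% | 9.4% |
| 9 | 6.8% | 26.2% | 21.3% |

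With 15% dropout the last-visit rate was 6.7% (3 visits) and 7.5% (4 visits). With skewed data and 3 visits it was 6.9%. The difference averaged over visits rejected in 6.2% to 7.7%.

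**Arithmetic check.** The mean standard error was 0.91 to 0.98 of the true SD of the estimate. If the ratio is r, the test in effect uses a critical value of 1.96 × r, where t on 48 degrees of freedom needs 2.01.
- 4 visits, complete data, r = 0.968: 1.96 × 0.968 = 1.897; P(|t48| > 1.897) = 6.4% (simulated 6.6%).
- 4 visits, 15% dropout, r = 0.931: 1.96 × 0.931 = 1.825; P(|t48| > 1.825) = 7.4% (simulated 7.5%).

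The interval widths relative to what is needed are 1.897/2.011 = 0.94 and 1.825/2.011 = 0.91, so the intervals are roughly 6% to 9% too narrow.

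**What drives it.** With 3 visits, an independence matrix in place of unstructured gave 6.1% for the single contrast, against 5.9%. The cause is the uncorrected variance and the normal reference.

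**After correction.** A Mancl-DeRouen sandwich with t on 48 degrees of freedom gave 3.9% to 5.3% for single or averaged contrasts wherever the unstructured fit was reliable.

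**Whether the unstructured matrix can be fitted.** With 9 visits and exchangeable correlation 0.6 it failed in 14 of 2,000 trials. With AR(1) 0.8 it was unusable in 1,779 of 2,000 (89%) with complete data and 1,848 of 2,000 (92%) with 15% dropout. This is one implementation, so it is indicative only.

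**Missing at random.** Three visits and no true difference; control subjects with a poor Day 7 value tend to miss Day 30 (about 32-36% missing, against 5% on Furoscix; assumed).

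| Day 30 SD (baseline SD = 1) | Bias, unstructured | Bias, independence |
|---|---|---|
| 1.0 | −0.001 | +0.085 |
| 1.6 | +0.09 | +0.24 |

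In the second case, at 2,040 subjects, unstructured GEE (+0.076) matched maximum likelihood (+0.074). The bias left there is therefore not peculiar to GEE. That comparison rests on 12 large simulated trials.

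**The case against.** The strongest reply is that the SAP never specifies an uncorrected sandwich. A reader might infer that it does, but the documents name only GEE and a covariance structure, so a programmer could apply a correction without departing from the text. That stands: the defect is an omission, and the 6-8% is conditional on the usual execution. It still matters, because the plan as written permits that execution and nothing in it points elsewhere.

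The study is also a declared pilot: "Given the exploratory nature of this study, no formal power analysis of sample size was conducted". With no multiplicity adjustment and analyses in both ITT and PP populations, these p-values never carried confirmatory weight. An inflation of one to three points is small beside that, and sandwich bias affects standard errors rather than the point estimates that guide pivotal planning. This limits the impact and is accepted. It does not justify intervals known to be too narrow when the remedy is cheap.

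Three stronger readings are tempting and not supported:
- That these analyses are valid only if data are missing completely at random. With an identity link and an unstructured matrix, bias under the tested mechanism was nil or equal to that of likelihood. The worry belongs to fallback structures such as independence.
- That the unstructured matrix shrinks the p-values. Independence gave nearly the same single-contrast rate. The weakness of the unstructured matrix is instability at nine visits.
- That planned results carry a false-positive rate above 20%. Those figures are for joint or interaction tests over nine visits, which the SAP does not name as reported efficacy results, and they apply only where the unstructured fit is obtained.

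SAP 7.1 does anticipate non-convergence, which partly answers the instability point. It leaves the order of fallback open.

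**Conclusion.** The point holds as a gap in specification with a modest, measurable consequence. Under empirical sandwich errors and a normal reference, tests of a visit-specific or averaged treatment difference reject about 6-8% under the null instead of 5%, and the intervals are slightly too narrow. Any joint or treatment-by-time Wald test would be worse: about 8-12% with three or four visits, and above 20% with nine.

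For the nine-visit endpoints, fallback is a realistic path, and an unordered list that includes independence leaves room for a data-driven choice and for bias under missingness at random. How often fallback would occur depends on the true correlation, which the documents do not give.

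The scope is NT-proBNP analysed on its own and nine secondary endpoints. The Finkelstein-Schoenfeld composite and the Wilcoxon test of days alive and event-free are untouched. The sizes rest on the assumed variance estimator, correlations and dropout; the direction and rough size agreed across separate simulations with different settings.

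**What to change.** In SAP 15.2.1.1 and 15.2.2, do one of the following:
- Keep GEE and specify a small-sample-corrected sandwich (for example Mancl-DeRouen) with a t reference and stated degrees of freedom. This option was simulated and restores roughly 5%.
- Use an MMRM fitted by REML with the same fixed effects and baseline covariate and Kenward-Roger degrees of freedom. This option was not simulated. An unstructured matrix at nine visits has 9 × 10/2 = 45 variance and covariance parameters, so it needs the fallback rule just as much.

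In SAP 7.1, replace the examples with a fixed order, for instance unstructured, then exchangeable, then AR(1), with independence last or removed. Require each table to state the structure used, and state the missing-data assumption that the repeated-measures analyses rely on.

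The cost is SAP wording and an option or procedure change in the software already named. No new data are needed. P-values and confidence intervals become slightly less favourable.

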4. SELECTION OF STUDY POPULATION

4.1. Inclusion Criteria

Female and male Subjects are eligible for inclusion only if all the following criteria are met:

1. Age 18 years or older.
2. Diagnosis of symptomatic chronic heart failure (NYHA Class II-IV) with background loop diuretic therapy for at least 4 weeks.
3. Need for augmented diuresis outside of the acute care setting as determined by the investigator.
4. On background therapy including daily total furosemide equivalent dose (40-160 mg) of loop diuretic or equivalent.
5. The subject must have signs of volume expansion, defined as two or more of the following six signs:
 - a) jugular venous distention
 - b) edema ($\geq 1+$)
 - c) ascites
 - d) pulmonary congestion on chest x-ray
 - e) pulmonary rales
 - f) NT-proBNP ≥ 1000 pg/ml (1400 for patients in atrial fibrillation) or, for patients not on Entresto, BNP ≥ 200 (400 for patients in atrial fibrillation)
6. Increase over the preceding 30 days in at least one of the following symptoms characteristic of worsening heart failure:
 - a) dyspnea
 - b) fatigue
 - c) exercise intolerance
7. Adequate environment for at home administration of Euroscix by patient or caregiver.

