6.2.1. Screening (Day 0)

The initial Screening assessment will be conducted the same day as the start of the Treatment Phase.

The following procedures/assessments will be performed at Screening:

- Informed consent (must be done prior to **any** of the following procedures)
- Eligibility review
- Medical history and Subject demographics (date of birth, gender, ethnic origin and race)
- Limited Physical Exam including NYHA Classification
- Composite Congestion Score (CCS)
- 5-point Current Dyspnea Score (using the script - [Appendix 7](#))
- Weight and height (Calculate BMI)
- Vital Signs
- % Lung Fluid Measurement (ReDS)
- Venous blood for clinical chemistries, hematology (run locally for eligibility), NT-proBNP (run locally for eligibility; 2nd sample sent to a centralized laboratory for subjects who qualify to participate)
- Urine pregnancy test on females of childbearing potential
- Administer the Kansas City Cardiomyopathy Questionnaire (KCCQ-12)
- Administer the patient global assessment visual analog scale (VAS)
- Administer Six Minute Walk Test (6MWT)
- Assess for adverse events
- Record concomitant medications (all medications taken within 48 hours)
- Schedule next study visit (Day 1).

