6.2.19. Patient Global Assessment Visual Analog Scale

The patient global assessment visual analog scale is a patient reported assessment of how good or bad a patient feels their health is that day. It is reported on a visual scale of 0-100 with 100 being the best health they can imagine and 0 being the worst health they can imagine. The EQ-VAS tool will be utilized for this assessment. This patient reported assessment will be obtained on Days 0-7, Day 17 and Day 30. This assessment should be done in the morning at approximately the same time as weight is being measured.

6.2.20. 5-Point Current Dyspnea Score

The 5-Point Current Dyspnea Questionnaire is a single-item, self-administered instrument that quantifies current symptoms of dyspnea (see [Appendix 5](#)). This will be administered after a verbatim script is read by study staff (see [Appendix 7](#)). This assessment will be done on Days 1, 2, 3, 4, 5, 6, 7, 17 and 30 and during an unscheduled in-clinic or phone visit.

6.2.21. 7-Point Dyspnea Score

The 7-Point Dyspnea Questionnaire is a single-item, self-administered instrument that quantifies changes in dyspnea symptoms since initiation of study product (see [Appendix 6](#)). This will be administered after a verbatim script is read by study staff (see [Appendix 7](#)). This assessment will be done on Days 1, 2, 3, 4, 5, 6, 7, 17 and 30 and during an unscheduled in-clinic or phone visit.

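### The 7-point dyspnea model is the only GEE in the SAP without a baseline covariate, although a suitable one, the Day 0 5-point dyspnea score, is already collected

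*SAP*

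**What the plan says.** The SAP's secondary analysis section (15.2.2) says: "A repeated measures analysis of 7-point Dyspnea Score across follow-up timepoints will be analyzed using a GEE model with treatment arm". The remaining terms are timepoint and the arm-by-time interaction, and the sentence stops there. The 5-point dyspnea model just above it has the same terms plus the baseline 5-point score. The models for VAS, congestion score, KCCQ-12, creatinine, weight, walk distance and ReDS (15.2.2) and for NT-proBNP (15.2.1.1) also carry their baseline value. That makes nine GEE models with a baseline term and one without.

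Protocol Appendix 6 shows why. The 7-point item asks the subject to compare breathing now with breathing just before entering the study, and it is scheduled from Day 1.

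The 5-point score is a rating of current dyspnea. The screening list in Protocol 6.2.1 includes it (the entry begins "5-point Current Dyspnea Score (using the script"), and the Protocol's Time and Events Schedule marks it on Day 0. Under Protocol 6.2.2, randomization follows completion of screening. Protocol 6.2.20, however, says of the 5-point score "This assessment will be done on Days 1, 2, 3, 4, 5, 6, 7, 17 and 30", which leaves Day 0 out.

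On design, SAP section 2 gives 34 versus 17 subjects, and Protocol 5.3.1 describes the allocation only as 2:1, with no stratification factor. SAP section 15 says: "Statistical tests will be performed at a two-sided alpha level of 0.05, unless otherwise specified".

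**The concern.** How much better a subject can report feeling plausibly depends on how breathless the subject was at entry. Inclusion criterion 6 requires "Increase over the preceding 30 days in at least one of the following symptoms characteristic of worsening heart failure", and fatigue or exercise intolerance meets it as well as dyspnea. The 5-point scale in Appendix 5 has a category for no shortness of breath. Entry dyspnea may therefore vary widely, and subjects at the low end have little room to improve.

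Nothing in the described allocation balances entry dyspnea between arms, and the planned model does not adjust for it. Two things are at stake for this endpoint: a shift in the estimated treatment difference if the 17 controls happen to differ from the 34 treated subjects at entry, and residual variance that an available covariate could remove.

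**Working it through.** **Inputs.** 34 and 17 subjects (SAP sections 2 and 4; 51 × 2/3 = 34 and 51 × 1/3 = 17, as stated). Two-sided alpha 0.05 (SAP 15). There is no power figure to reproduce: "Given the exploratory nature of this study, no formal power analysis of sample size was conducted". The correlation r between the Day 0 5-point score and the follow-up 7-point score is not in the documents, so I vary it from 0 to 0.5. The formulas treat one timepoint with normal outcomes, as an approximation to the GEE treatment contrast.

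**Step 1: chance imbalance in entry dyspnea.** SE = sqrt(1/34 + 1/17) = 0.297 SD. The probability of an absolute difference above 0.3 SD is 31%. Above 0.5 SD, z = 0.5/0.297 = 1.68 and the probability is 9.2%.

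**Step 2: effect of an imbalance on the unadjusted estimate.** Shift = imbalance × r, in outcome SDs. At an imbalance of 0.5 SD this is 0.5 × 0.3 = 0.15 SD, or 0.5 × 0.5 = 0.25 SD. At r = 0 it is zero.

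**Step 3: variance with and without the covariate.** The ratio of adjusted to unadjusted variance is (1 − r²) × (1 + 1/47). The second factor is the expected cost of estimating the slope: 51 subjects less two arm means leave 49 degrees of freedom, and 49 − 2 = 47. The difference detectable with 80% power, a yardstick chosen here for illustration, is (1.960 + 0.842) × 0.297 = 0.832 SD unadjusted. The adjusted value is that times the square root of the variance ratio.

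| r (assumed) | 1 − r² | Variance ratio | Change | Detectable difference, adjusted (SD) | Power at 0.832 SD |
|---|---|---|---|---|---|
| 0 | 1.000 | 1.021 | +2% | 0.841 | 79.2% |
| 0.1 | 0.990 | 1.011 | +1% | 0.837 | 79.6% |
| 0.2 | 0.960 | 0.980 | −2% | 0.824 | 80.8% |
| 0.3 | 0.910 | 0.929 | −7% | 0.802 | 82.8% |
| 0.4 | 0.840 | 0.858 | −14% | 0.771 | 85.7% |
| 0.5 | 0.750 | 0.766 | −23% | 0.728 | 89.3% |

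Break-even is where (1 − r²) × 48/47 = 1, so r² = 1/48 and r = 0.144. As an effective gain in subjects, 1/0.929 gives about 8% and 1/0.766 about 31%.

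**Step 4: type I error.** This was simulated with no treatment effect, 34 versus 17 subjects and 40,000 trials per value of r, comparing a t-test with ANCOVA.

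| r | All trials, unadjusted | Imbalance ≥ 0.5 SD, unadjusted | Imbalance ≥ 0.5 SD, adjusted |
|---|---|---|---|
| 0 | 5.1% | 5.2% | 5.2% |
| 0.3 | 4.8% | 8.2% | 5.3% |
| 0.5 | 5.0% | 15.4% | 5.5% |

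The simulated SDs of the adjusted and unadjusted estimates confirm step 3: (0.3009/0.2979)² = 1.020, (0.2858/0.2959)² = 0.933 and (0.2607/0.2973)² = 0.769.

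**The case against.** The strongest reply is that nothing here is an error. The SAP adjusts each GEE endpoint for its own baseline, the 7-point item has none, and the item already refers back to entry status. Randomization makes the unadjusted comparison valid, and step 4 bears that out. The trial is a pilot without a power analysis, this is one of ten secondary endpoints, and a baseline-adjusted dyspnea comparison already exists in the 5-point model. Adding the covariate also has a cost: the SAP does not impute, so a subject without a Day 0 score would drop out of the 7-point model, which today needs no Day 0 value.

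Much of that stands. It explains the omission and keeps the point modest. It does not remove the case for the covariate. SAP 15.2.2 compares every secondary endpoint at the 0.05 level, and refining analytical methods for a pivotal trial is a stated objective (SAP 6.2). The Day 0 score is required by both the screening list and the Protocol schedule, so few should be missing. The same subjects would already be lost from the 5-point change-from-baseline model.

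A reader might also infer from inclusion criterion 6 that some subjects cannot report marked improvement. The documents do not show this. The criterion concerns a recent increase in a symptom, so a subject who qualifies on fatigue may still be breathless. The Appendix 7 script also asks about limitation in everyday tasks before the breathing question. Limited room to improve is a plausible reason for a correlation, not an established fact.

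**Conclusion.** The point holds as one of efficiency and conditional bias for a single secondary endpoint. The planned model leaves a chance imbalance in entry dyspnea uncorrected; one above 0.5 SD has about a 9% chance, and at exactly 0.5 SD it would shift the estimate by 0.15 to 0.25 SD for r of 0.3 to 0.5. Precision is likely lost if r exceeds about 0.14. The cost of adjusting when r is zero is about 2% in variance, against a reduction of about 7% to 23% at r of 0.3 to 0.5. All of this rests on an assumed r and a single-timepoint normal approximation.

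Three stronger readings are not supported:

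- That the unadjusted test is invalid. Its error rate over all randomizations is about 5%. The 8.2% and 15.4% apply only within the minority of trials with a large imbalance.
- That precision is certainly lost. The documents give no correlation.
- That the Day 0 score is in jeopardy because 6.2.20 omits it. Protocol 6.2.1 and the schedule both require it, and the SAP's 5-point model uses it. The omission is a minor inconsistency to reconcile.

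**What to change.** In SAP 15.2.2, add the Day 0 5-point Current Dyspnea Score as a covariate in the 7-point model, entered as it is in the 5-point model. Keep the present unadjusted model as a pre-specified sensitivity analysis, so that subjects without a Day 0 score still contribute somewhere. Report the observed correlation between the Day 0 score and the 7-point score, which would help in planning the pivotal trial.

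In Protocol 6.2.20, bring the day list into line with 6.2.1 and the Time and Events Schedule, both of which include Day 0.

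The cost is a phrase in the SAP, a short protocol correction, one degree of freedom, and the loss from the adjusted model of any subject missing the Day 0 score. No new data are needed.
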